4.8 Subject Coding

Each Clinical Investigation Center will have a list containing the identification codes to be assigned to enrolled subjects. Since enrollment will be competitive, each list will contain 30 identification codes.

At the time of enrollment, each subject will be sequentially assigned such an identification code.

Lists with complex alphanumeric identification codes will be generated by GUNA S.p.a. through

The complex alphanumeric code complies with the current Privacy Regulations regarding the coding of subjects participating in clinical studies.

4.9 Procedures

4.9.1 Evaluations of Time Points

Baseline (T0): Enrollment and initiation of infiltrative treatment.

Week 1 (T1): Second infiltrative treatment.

Week 2 (T2): Third infiltrative treatment.

Week 3 (T3): 1st follow-up visit + fourth infiltrative treatment.

Week 4 (T4): Fifth infiltrative treatment.

Week 6 (T6): 2nd follow-up visit.

Week 16 (T16)/FU: 3rd follow-up visit.

4.9.2 Visit Schedule

Baseline (T0): Enrollment

During routine clinical practice, the Investigators participating in the Clinical Investigation will select subjects diagnosed with symptomatic thumb carpometacarpal osteoarthritis. The Principal Investigator will be responsible for the correct clinical diagnosis, also utilizing the instrumental exams specified in the Investigation Plan. Subjects meeting the selection criteria will be identified. After thoroughly explaining the purposes, objectives, and procedures outlined in the Investigation Plan, the subject will be invited to participate in the Investigation. The selected subject will be invited to review the information sheet and date and sign the Informed Consent and Personal Data Processing Consent

form. Female subjects must provide evidence of a negative pregnancy test to be enrolled. The examination will then proceed, along with the collection of information required by the electronic Data Collection Form (e-CRF) appropriately prepared.

This will be followed by:

- VAS assessment;
- DASH assessment;
- FIHOA assessment;
- Pinch Strength Test assessment using a dynamometer.

The first intra/peri-articular infiltration of MD-Small Joints Collagen Medical Device (see § 4.12) will then be performed, evaluating any Adverse Events in the moments following administration. Any previous or ongoing pharmacological treatments of any kind (concomitant medications) will be documented in the annotations section of the e-CRF. During the study, systemic and topical analgesic medications may be used in case of severe pain. Investigators will explain to enrolled subjects that such medications should only be used if absolutely necessary and will provide each subject with 1 package of oral analgesic medication and 1 package of topical analgesic medication among those permitted (see table 1), explaining the possible adverse events associated with intake or application and ensuring, under their responsibility, that the subject can take or apply the provided medication. To monitor its consumption, each subject will be given a clinical diary in which to record the day and dose of medication used, reminding them that such medications should not be taken or applied within 24 hours before each visit.

PERMISSIBLE ORAL MEDICATIONS	PERMISSIBLE TOPICAL MEDICATIONS
Paracetamol 1000 mg. cpr.	Diclofenac 2% gel
Etoricoxib 60 mg. cpr.	

Tab. 1 Permissible topical analgesic medications

The enrolled subject will be assigned a complex alphanumeric identification code. The collected data must be entered into the e-CRF within the following 48 hours.

T1 settimana (± 1 gg):

At one week from T0, the second intra/peri-articular infiltration of MD-Small Joints Collagen Medical Device will be performed (see § 4.12), and the use of the analgesic medication will be evaluated through the analysis of the clinical diary. Any adverse events occurring after the first administration will also be assessed.

T2 weeks (±1 day):

At two weeks from T0, the third intra/peri-articular infiltration of MD-Small Joints Collagen Medical Device will be performed (see § 4.12), and the use of the analgesic medication will be evaluated through the analysis of the clinical diary. Any adverse events occurring after the second administration will also be assessed.

T3 weeks (±1 day):

At three weeks from T0, the fourth peri-articular infiltration of MD-Small Joints Collagen Medical Device will be performed (see § 4.12), and the use of the analgesic medication will be evaluated through the analysis of the clinical diary. The evaluation of VAS will be conducted. Any adverse events occurring after the third administration will also be assessed. The collected data must be entered into the e-CRF within the subsequent 48 hours.

T4 weeks (±1 day):

At four weeks from T0, the fifth and final peri-articular infiltration of MD-Small Joints Collagen Medical Device will be performed (see § 4.12), and the use of the analgesic medication will be evaluated through the analysis of the clinical diary. Any adverse events occurring after the fourth administration will also be assessed.

6 weeks (±2 days):

At six weeks from T0, and two weeks after the end of infiltrations, the following evaluations will be performed:

- VAS assessment;
- DASH assessment;
- FIHOA assessment;
- Pinch Strength Test evaluation using dynamometer;
- evaluation of the use of analgesic medication through the analysis of the clinical diary;

assessment of any adverse events occurring after the fifth administration. The collected data must be entered into the e-CRF within the subsequent 48 hours.

T16 weeks/FU (±7 days):

At four months from enrollment, and twelve weeks after the end of infiltrations, the following evaluations will be performed again:

- VAS assessment;
- DASH assessment;
- FIHOA assessment;

- Pinch Strength Test evaluation using dynamometer;
- evaluation of the use of analgesic medication through the analysis of the clinical diary;

assessment of any adverse events occurring between T6s and T16s/FU. The collected data must be entered into the e-CRF within the subsequent 48 hours.

The scales, questionnaires, and tests used to determine the performance of the medical device under investigation (VAS, DASH, FIHOA, and Pinch Strength Test) will be administered to the subject by the Principal Investigators or Co-Investigators. The recording of data from the clinical diary regarding the intake of analgesic medication will be carried out by them.

In the e-CRF, the medications taken for the treatment of any co-morbidities that emerge during the Clinical Investigation must also be recorded.

At each visit, the occurrence of Adverse Events will be carefully evaluated. All Adverse Events (AE) and Serious Adverse Events (SAE) appearing between the date of Informed Consent signature and the end of the Clinical Investigation will be recorded and reported.

All data collected must be entered into the electronic Data Collection Form (e-CRF) provided by Guna S.p.a. Principal Investigators, Co-Investigators, or designated Data Managers will be responsible for the correct entry of the collected data into the e-CRF.

In particular, it is expected to obtain a data collection that is schematically described in the following table (tab. 2), which lists the registrations to be made at each visit.

EXPERIMENTAL PROCEDURES "SMAGENART PILOT STUDY"	VISIT T0 Enrollment	VISIT T1s. ± 1day	VISIT T2s. ± 1day	VISIT T3s. ± 1day	VISIT T4s. ± 1day	VISIT T6s. ± 2day	VISIT T16s/ FU ± 7day
Clinical diagnosis of rhizarthrosis confirmed radiographically	X						
Evaluation of selection criteria	X						
Sign Informed Consent	X						
Sign Privacy Consent	X						
Collection of socio-demographic data	X						
Medical history collection	X						
VAS assessment	X			X		X	X
DASH assessment	X					X	X
FIHOA assessment	X					X	X
Pinch Strength Test Evaluation	X					X	X
Infiltrative treatment	X	X	X	X	X		
Clinical diary evaluation of analgesic consumption.		X	X	X	X	X	X
Concomitant treatment for ongoing	X	X	X	X	X	X	X

comorbidities							
Adverse Event Assessment (AE/SAE)	X	X	X	X	X	X	X

Tab.2 Procedures and data collection during the Clinical Investigation

4.10 Material necessary for conducting the Clinical Investigation

The medical device necessary to conduct the investigation is MD-Small Joints Collagen Medical Device (GUNA, Milan-Italy) marketed in 2ml vials.

This device and the auxiliary drugs provided will be sent by Guna S.p.a. to the pharmacy of the Clinical Investigation Centers with shipment at a controlled temperature (range 4°-25°C) and monitored through dataloggers, in quantities suitable for conducting the Investigation.

Medical devices and auxiliary drugs must be stored by the pharmacy of the Clinical Investigation Centers within the same temperature range. Each Clinical Investigation Center will be equipped with a datalogger provided by the Sponsor for temperature monitoring.

The pregnancy tests will be sent, in suitable quantities, to the pharmacy of the Clinical Investigation Centers together with the medical devices and auxiliary drugs.

4.11 Group in the study

The Investigation Plan envisages a single experimental group which will be treated with infiltrations of: MD-Small Joints Collagen Medical Device (GUNA, Milan-Italy).

Composition per 2ml: collagen of porcine origin 100 µg

Excipients: Violet, NaCl, Water for injection.

The subjects will be treated with 1 infiltration with a volume of 2ml at the time of enrollment (T0) and on a weekly basis for a total of 5 infiltrations.

4.12 Infiltration Technique

The infiltrations will be performed using 2.5ml syringes and 26 gauge/13mm needles under complete aseptic conditions. The first 3 infiltrations will be carried out at both intra- and peri-articular levels by injecting MD-Small Joints Collagen Medical Device into the trapeziometacarpal joint until a counter-pressure is felt, preventing further penetration of the liquid; the remaining quantity (usually about 1ml) will be injected at the peri-articular level by retracting the needle tip.

The fourth and fifth infiltrations will be performed only at the peri-articular level.

4.13 Efficacy Criteria

4.13.1 Primary Endpoint

The primary endpoint will consist of evaluating, through the Visual Analogue Scale (VAS), the performance of MD-Small Joints Collagen Medical Device in reducing pain associated with trapeziometacarpal osteoarthritis at T6 weeks (T6s) compared to T0. A reduction in VAS score of at least 30% is considered clinically significant.

4.13.2 Secondary Endpoints

The secondary endpoints will include evaluating the performance of MD-Small Joints *Collagen Medical Device* through:

- VAS at T3s and T16s/FU compared to T0;
- DASH at T6s and T16s/FU compared to T0;
- FIHOA at T6s and T16s/FU compared to T0;
- Pinch Strength Test at T6s and T16s/FU compared to T0;
- Consumption of analgesics during various stages of the study;
- Incidence of Adverse Events.

4.13 Data Collection

All data resulting from the Clinical Investigation must be entered, within two days of their collection, into the electronic Data Collection Form (e-CRF) "Pheedit Dedagroup" provided by the Sponsor. Radiographic data will be collected and stored digitally on the hospital portal. Data entry procedures will be performed by the Principal Investigators, Co-Investigators, or the designated Data Manager.

4.14 Early Termination of the Investigation

Subjects may terminate the Investigation prematurely for the following reasons:

- a. at their request (even without providing a reason);
- b. at the discretion of the investigator;
- c. if they experience an Adverse Event.

The reason for termination will be recorded in the e-CRF.

[figure not shown]
4 STATISTICS

5.1 Sample Size

It is assumed that the fraction of subjects who will spontaneously reduce the VAS scale value by 30%, given their clinical characteristics, cannot exceed 20% of those enrolled (null hypothesis: $p_0 \leq 0.2$). Additionally, it is assumed that to consider the treatment with MD-Small Joints Collagen Medical Device clinically effective, the fraction of subjects who will reduce the VAS scale value by at least 30% should be at least 50% (alternative hypothesis: $p_a \geq 0.5$).

With these assumptions, using a two-tailed binomial test, the sample size will be 33 subjects, with a power of 95.99% and an alpha error of 2.75%. Assuming that dropouts are approximately 20%, the number of subjects to be recruited will be approximately 42 ($\frac{33}{(1-0.2)} = \frac{33}{0.8} \approx 42$).

Incidentally, the null hypothesis can be rejected after obtaining 12 or more clinical successes, and the alternative hypothesis can be rejected with 1 or fewer clinical successes.

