4.7 Selection Criteria

4.7.1 Inclusion Criteria:

- Male and female subjects aged between 18 and 75 years;
- Subjects with clinically diagnosed symptomatic thumb carpometacarpal osteoarthritis confirmed radiographically (stages I and II according to Eaton and Littler's classification);
- [N.B. in case of bilateral symptomatic thumb carpometacarpal osteoarthritis, treatment can be unilateral only, at the level of the thumb carpometacarpal joint that is more affected at the time of enrollment].
- Subjects with a VAS score ≥ 5 ;

[The request for pain intensity (VAS) from the patient should refer to moments of hand use, not at rest!]

- Subjects with joint pain for at least 1 month;
- Subjects not using thumb carpometacarpal orthotic devices;
- Subjects agreeing not to take analgesics within 24 hours before the scheduled visits;
- Subjects capable of understanding and signing the Informed Consent.

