6.8 Data Processing and Publication

The results of this study will be summarized and presented in a final report aimed at drawing reliable conclusions regarding the performance of the injectable medical device MD-Small Joints Collagen Medical Device in the treatment of trapeziometacarpal osteoarthritis. The scientific article will then be drafted and submitted to a peer-reviewed journal in the field for publication to disseminate the obtained results to the scientific community.

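### The VAS reading that admits a subject appears also to be the baseline for the 30% fall, and an unsourced 20% null rate is the only allowance for regression to the mean

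*Protocol*

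**What the plan says.** All references are to the protocol.

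- **Entry.** Section 4.7.1 requires "Subjects with a VAS score ≥ 5", asked about pain during hand use, and "Subjects with joint pain for at least 1 month".
- **Timing.** Section 4.9.1 describes the first visit as "Baseline (T0): Enrollment and initiation of infiltrative treatment". Table 2 marks the selection criteria, both consents, a VAS assessment and the first infiltration in the T0 column. The next VAS is at week 3. No screening visit, run-in or repeat baseline is scheduled.
- **Endpoint.** Sections 4.13.1 and 5.1.3 take the fraction of subjects whose VAS at week 6 is at least 30% below T0, with a Clopper-Pearson 95% interval.
- **Comparator.** Section 4.11 provides one treated group. Section 5.1 supplies the null rate: "It is assumed that the fraction of subjects who will spontaneously reduce the VAS scale value by 30%, given their clinical characteristics, cannot exceed 20" (per cent, among enrolled subjects). The alternative is that "the fraction of subjects who will reduce the VAS scale value by at least 30% should be at least 50"%.
- **Test.** Section 5.1 continues: "using a two-tailed binomial test, the sample size will be 33 subjects, with a power of 95.99% and an alpha error of 2.75"%. It rejects the null at 12 or more successes.
- **Use.** Section 6.8 plans a report "aimed at drawing reliable conclusions regarding the performance of the injectable medical device".

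**The concern.** VAS pain varies from visit to visit. If a subject is admitted because one reading is 5 or more, and the fall is measured from that same reading, those admitted on a chance high will tend to read lower at week 6 with no treatment effect. A control group would show the same drift and cancel it. Here there is none, so the assumed 20% has to absorb all of it, along with natural fluctuation and any other improvement not due to the device.

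The 20% is supported only by a reference to the subjects' clinical characteristics. If the true untreated rate in this selected group is higher, the test rejects more often than its stated alpha, and a report meant to support conclusions about device performance would rest on that rejection. A later analysis plan cannot repair this, because it cannot create a second pre-treatment reading.

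**Working it through.** **1. The plan's own figures.** Inputs from section 5.1: n = 33, reject at 12 or more, p0 = 0.2, pa = 0.5, dropout 20%.

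- Upper tail: P(X ≥ 12 | 33, 0.2) = 0.0216.
- Lower tail: P(X ≤ 1 | 33, 0.2) = 0.0059.
- Two-tailed alpha: 0.0216 + 0.0059 = 0.0275, as stated.
- Power: P(X ≥ 12 | 33, 0.5) = 0.9599, as stated.
- Recruitment: 33/0.8 = 41.25, rounded up to 42, as stated.

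The arithmetic is correct. What remains is the input p0.

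**2. How far alpha depends on p0.** Chance that an inert device gives at least 12 successes of 33:

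| True untreated responder rate | P(X ≥ 12) |
|---|---|
| 20% | 2.2% |
| 25% | 9.9% |
| 30% | 26.7% |

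If all 42 were analysed (15 or more successes needed for an upper tail of at most 2.5%), the figures would be 1.3%, 8.1% and 25.7%.

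**3. How regression to the mean produces responders.** With population mean m, visit-to-visit correlation r and no true change, the expected week-6 value for a T0 reading x is m + r(x − m). For m = 5, r = 0.5 and x = 7 this is 5 + 0.5 × 2 = 6. Success needs 0.7 × 7 = 4.9 or less. The expected distance to success shrinks from 7 − 4.9 = 2.1 points to 6 − 4.9 = 1.1.

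**4. Size under assumed values.** The documents give no VAS mean, SD or correlation, so all of these are assumptions: true pain normal with mean 5 to 6 and between-subject SD 1.5; independent visit error with SD s; readings clipped to 0–10; admission at 5 or more; no change over time; success if week 6 ≤ 0.7 × baseline. The correlation is 1.5²/(1.5² + s²), so s = 0.5, 0.75, 1.0 and 1.5 give 0.90, 0.80, 0.69 and 0.50.

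| Correlation (about) | One shared reading | Separate baseline reading |
|---|---|---|
| 0.9 | below 1% | below 1% |
| 0.8 | 3–5% | 2–3% |
| 0.7 | 8–13% | 6–8% |
| 0.5 | 19–26% | 14–17% |

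**5. A wider grid.** With source-population mean 4 to 6, total SD 2.0 to 2.5 and correlation 0.4 to 0.9, the shared-reading share ran from about 1% to 43%. It exceeded 20% in about 16 of 36 settings, all at correlation 0.7 or lower. At mean 5, SD 2.5 and correlation 0.5 it was 30%, giving a 27% chance of reaching 12 of 33; a separate baseline brought the share to 20%. A separate baseline lowered the share in every setting, by about 1 to 17 percentage points.

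**The case against.** The strongest reply is that section 5.1 defines the null rate among those enrolled. Enrolled subjects have already passed the VAS threshold, so a correct p0 would include regression to the mean. This stands: a reader might infer that 20% is too low or that the test is anti-conservative, and the documents show neither. At a correlation of 0.8 or more, regression alone stays well under 20% in both sets of assumptions. What remains is that the figure is unsourced, and that section 5.1 does not say whether selection on the baseline value was considered.

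Second, the shared reading is inferred. Section 4.9.2 has eligible subjects identified before consent and lists the VAS assessment after the examination, so a separate qualifying reading could be meant. But Table 2 schedules no other pre-treatment VAS, and section 6.3 bars any study activity before consent. One reading is the natural inference, though nowhere stated.

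Third, the other entry rules might be read as selecting subjects about to improve. The text does not go that far. One month of pain is a minimum, in radiographically confirmed disease. In bilateral cases the more affected joint is chosen, but by no stated VAS rule. Recent users of anti-inflammatory drugs are excluded, but nobody is told to stop them.

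Fourth, untreated responder shares of 36% to 46% can be generated, but only by adding an assumed untreated improvement of 0.5 or 1.0 point. That is not a selection effect, and a separate baseline would not remove it.

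Finally, this is openly a single-arm pilot, and section 5.1 ties clinical effectiveness to at least 50%. Yet the rejection rule operates at 12/33 = 36.4%, and section 6.8 looks for conclusions about performance. The pilot label tempers the point but does not remove it.

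**Conclusion.** The concern holds in a limited form. As scheduled, the qualifying VAS and the baseline VAS appear to be one reading, so regression to the mean can count as response in a trial with no control. The stated alpha of 2.75% is right only if the untreated rate among those enrolled is 20%. At 25% or 30%, the chance of a false rejection in the upper tail rises from 2.2% to 9.9% or 26.7%.

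Whether regression alone could bring the rate that high depends on a correlation that the documents do not give. Under the narrower assumptions in step 4, the 20% is crossed only somewhere between correlations of 0.7 and 0.5. It would be wrong to conclude that the 20% is too low, or that a positive result would be spurious. The supported conclusion is that the design leaves an avoidable source of apparent response in place, and that rejecting 20% cannot by itself attribute the change to the device.

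**What to change.** 1. **Sections 4.7.1 and Table 2.** Apply the VAS ≥ 5 criterion to a reading at a consented contact before T0. Take a separate VAS at T0, before the first injection, and use it as the baseline whatever its value. Cost: one extra short scale, an earlier consent step and some delay before the first injection. This reduces regression to the mean but does not remove untreated improvement.

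2. **Sections 5.1 and 6.8.** State that rejecting 20% shows a before-after responder fraction above an assumed spontaneous rate, not an effect attributable to the device. Report the planned Clopper-Pearson lower limit beside reference rates of 20%, 25% and 30%, as a sensitivity display. With 33 analysed, the limit clears these at 12, 14 and 16 successes. Cost: a more modest conclusion, and no added subjects.

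No new rate should become a pass/fail gate. Requiring the lower limit to clear 35%, for example, would need 18 of 33 and would cut power at a true rate of 50% from 96.0% to 36.4%.

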4.5 Participant Population

A total of 42 subjects with thumb carpometacarpal osteoarthritis will be enrolled. The recruitment phase will not be closed until the number of subjects specified in the Clinical Investigation Plan is reached.

Only subjects who meet the following criteria will be included:

- Belonging to the Clinical Investigation Centers.

- Meeting the inclusion criteria and not presenting exclusion criteria.
- Having dated and signed the Informed Consent.

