5.1.3 Primary Endpoint

Tutti i dati saranno validati con delle opportune regole in base alle loro caratteristiche, e quindi sottoposti alle normali analisi descrittive (media, mediana, moda, deviazione standard, errore standard della media, valore minimo e massimo, range interquartile). Le variabili continue distribuite in modo Gaussiano saranno rappresentate da media \pm deviazione standard, mentre quelle non

Gaussiane saranno rappresentate da mediana e range interquartile. Le variabili categoriche saranno descritte con tabelle di frequenza relativa ed assoluta.

The primary endpoint will be determined by the fraction of enrolled subjects who reduce the VAS scale value by at least 30% after 6 weeks (T6s) from the start of treatment. The percentage fraction will be calculated with its 95% confidence interval according to Clopper-Pearson.

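### The cut-off of 12 successes is right only for 33 analysed subjects, yet it is given without a denominator while 42 are enrolled and the endpoint is worded on enrolled subjects

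*Protocol*

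**What the plan says.** Section 5.1 (Sample Size) takes a null responder rate that "cannot exceed 20% of those enrolled" and an alternative of at least 50%, a responder being a subject whose VAS falls by at least 30%. It gives the design as a two-tailed binomial test in 33 subjects, with 95.99% power and 2.75% alpha. It continues: "Assuming that dropouts are approximately 20%, the number of subjects to be recruited will be approximately 42", from 33/0.8. Two thresholds close the section, neither with a denominator. The upper one reads: "the null hypothesis can be rejected after obtaining 12 or more clinical successes". The lower one reads: "the alternative hypothesis can be rejected with 1 or fewer clinical successes".

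Section 4.5 (Participant Population) states that "A total of 42 subjects with thumb carpometacarpal osteoarthritis will be enrolled" and keeps recruitment open until that number is reached.

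Section 5.1.3 (Primary Endpoint) sets the denominator: "The primary endpoint will be determined by the fraction of enrolled subjects who reduce the VAS scale value by at least 30" per cent at six weeks. For the analysis it says: "The percentage fraction will be calculated with its 95% confidence interval according to Clopper-Pearson". It does not say how the interval leads to a conclusion.

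**The concern.** A binomial critical value belongs to one sample size. Recruitment goes to 42, so exactly 33 subjects are analysed only if exactly 9 drop out. For any other number the protocol states no threshold except the bare count.

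The denominator is also inconsistent. Dividing 33 by 0.8 makes sense only if dropouts leave the denominator. The null and the endpoint, both worded on enrolled subjects, keep them in.

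At stake is the claim on the primary endpoint. With 34 or more in the denominator, a result of 12 successes could be reported as rejecting the null beside a 95% interval that still contains 20%, and the protocol does not say which governs. Left open, the choice could be made after the results are known.

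A smaller fault sits in the same sentence of section 5.1. One or fewer successes is said to reject the alternative, but the stated alpha is reached only by counting that outcome as rejecting the null.

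**Working it through.** **Inputs.** p0 = 0.20, pa = 0.50, n = 33, upper cut-off 12, lower cut-off 1, dropout 20% (section 5.1); 42 enrolled (section 4.5); 95% Clopper-Pearson interval (section 5.1.3). The protocol gives no nominal alpha. I assume 5% two-sided, to match the 95% interval.

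**Step 1: reproduce the plan at n = 33.**
- P(X ≥ 12 | 33, 0.2) = 0.02159
- P(X ≤ 1 | 33, 0.2) = 0.00586
- Sum = 0.02745, the stated 2.75%
- P(X ≥ 12 | 33, 0.5) = 0.95993, the stated 95.99%
- 33/0.8 = 41.25, rounded up to 42

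The plan's figures are correct at n = 33. The error of the upper cut-off alone is 2.16%; the remaining 0.59 points come from X ≤ 1.

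**Step 2: keep 12 fixed and change n.** Error = P(X ≥ 12 | n, 0.2) + P(X ≤ 1 | n, 0.2). The Clopper-Pearson lower limit for 12 of n is the 2.5% quantile of Beta(12, n − 11). The exact two-sided p-value sums all outcomes no more likely than the one observed.

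| n | Upper tail | Both tails | Lower limit for 12/n | Exact p for 12/n | Smallest count with lower limit above 20% |
|---|---|---|---|---|---|
| 33 | 2.16% | 2.75% | 20.40% | 0.027 | 12 |
| 34 | 2.74% | 3.23% | 19.75% | 0.032 | 13 |
| 35 | 3.44% | 3.83% | 19.13% | 0.053 | 13 |
| 36 | 4.24% | 4.57% | 18.56% | 0.058 | 13 |
| 37 | 5.17% | 5.44% | 18.01% | 0.065 | 13 |
| 38 | 6.23% | 6.45% | 17.50% | 0.101 | 14 |
| 40 | 8.75% | 8.90% | 16.56% | 0.116 | 14 |
| 42 | 11.82% | 11.92% | 15.72% | 0.176 | 15 |

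The count parts from the interval at n = 34 and from the exact 5% test at n = 35. Its own error exceeds 5% from n = 37, that is, with 5 or fewer dropouts. Count and interval disagree at exactly 12 successes for n = 34 to 37, at 12 or 13 for n = 38 to 41, and at 12 to 14 for n = 42. The lower cut-off is also specific to n: at 2.5% per tail it is 1 at n = 33 and 3 at n = 42.

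**Step 3: how likely is n above 33?** Assume that each of 42 subjects drops out independently, so completers follow Bin(42, 1 − d). At d = 20% the mean is 42 × 0.8 = 33.6.

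| Dropout d | P(exactly 33) | P(34 or more) | P(37 or more) |
|---|---|---|---|
| 20% | 14% | 53% | 13% |
| 15% | 8% | 83% | 38% |
| 10% | 1% | 98% | 76% |

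**Step 4: all 42 as denominator, dropouts as failures.** Assume that the 20% and 50% rates hold only among completers. The success probability is then 0.2(1 − d) under the null and 0.5(1 − d) under the alternative.

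| Dropout d | Error of X ≤ 1 or X ≥ 12 | Power at 15 of 42 |
|---|---|---|
| 20% | 3.4% | 76.4% |
| 15% | 4.7% | 85.2% |
| 10% | 6.5% | 91.5% |

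If instead half of all 42 respond, power at 15 of 42 is 97.8%.

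**The case against.** The best defence is that nothing is miscalculated and that the context ties 12 to 33. The sentence follows the 33-subject calculation, only n = 33 gives those alpha and power values, and it is introduced as an aside. A two-tailed binomial test is also named, and a named test can be applied at whatever n is observed. That reading of 12 is fair. It does not settle the matter: 33 analysed subjects are not assured, no threshold is given for another number, and the endpoint's denominator is not 33.

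A second defence is size, and much of it stands. At the planned dropout the error is about 3.4%, and exceeding 5% needs 37 or more analysed, a 13% chance. The 11.9% needs all 42 in the denominator with the 20% null holding among all of them; since a dropout without a week-6 VAS cannot be an observed success, that in practice means no dropouts. The conflict zone is narrow: under the 50% alternative, 12 to 14 successes of 42 has a probability of about 2%. At n = 34 the exact test still rejects, so the disagreement there is the ordinary gap between that test and Clopper-Pearson.

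A third defence is that dropout handling can be left to the SAP. Detail can be. Here, however, the protocol itself fixes a count and two incompatible denominators, and a SAP would have to contradict one of them.

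**Conclusion.** The concern holds. The sample-size figures are right for 33, but the cut-off as written is not valid for the trial as recruited, and the inflation to 42 contradicts a null and an endpoint worded on enrolled subjects. The effect on error is small at the planned dropout (2.75% rising to about 3.4%) and grows as dropout falls, with 11.9% as the no-dropout bound. The more likely harm is a conclusion left undecided because count and interval disagree, which becomes possible with 8 or fewer dropouts. These sizes rest on the assumed 5% two-sided level, independent dropout, and the null rates stated at each step. It should be corrected before the data are analysed. It does not undermine the choice of 33 or 42.

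**What to change.** 1. In section 5.1, give 12 as the critical value for 33 analysed subjects, as an illustration only.
2. Use one denominator in 5.1 and 5.1.3. If analysed subjects, reword the null and the endpoint. If enrolled subjects, state how dropouts count and recompute the power, because 33/0.8 is then not the right inflation.
3. State one rule that holds at the n actually analysed. Either the null is rejected if the lower limit of the two-sided 95% Clopper-Pearson interval exceeds 20% (12 of 33, 13 of 34 to 37, 14 of 38 to 41, 15 of 42), or a named exact binomial test is used with its alpha stated (two-sided 5%: 12 of 33 or 34, 13 of 35, 15 of 42).
4. Say whether one or fewer successes is part of the alpha, as 2.75% implies, or a separate futility remark. In the latter case the error of the upper cut-off is 2.16%.

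This is two or three sentences, with no new subjects or data. Compared with the fixed count, the interval rule asks for one more responder at n = 34 (power at 50% goes from 97.1% to 93.9%) and three more at n = 42. If dropouts are to count as failures among 42, power at the planned 20% dropout is 76.4% against the 95.99% stated, so the denominator should be chosen with that loss in view.

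### Section 5.1 presents 1 or fewer successes as the cut-off for rejecting the 50% alternative, but it is the lower critical value of the two-tailed test of 20%

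*Protocol*

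**What the plan says.** Section 5.1 (Sample Size) sets a null responder rate of at most 20% and an alternative of at least 50%, a responder being a subject whose VAS falls by at least 30%. It then gives the design: "using a two-tailed binomial test, the sample size will be 33 subjects, with a power of 95.99% and an alpha error of 2.75" per cent. With 20% dropout, 33 becomes 42 recruited.

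The section closes with two counts. Twelve or more successes reject the null hypothesis, and "the alternative hypothesis can be rejected with 1 or fewer clinical successes". No error rate is given for the second count.

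Section 5.1.3 (Primary Endpoint) plans the analysis of the responder fraction: "The percentage fraction will be calculated with its 95% confidence interval according to Clopper-Pearson".

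**The concern.** The two counts are presented as a matching pair, one for each hypothesis. Twelve is an exact critical value for 20%. One of 33 is an observed rate of 3%, far below anything needed to cast doubt on a true rate of 50%, so it looked unlikely to be a boundary for 50% at all.

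What is at stake is the reading of a low or intermediate result. Section 5.1 makes 50% the threshold for calling the treatment effective, and this clause is the protocol's only rule for declaring that threshold unmet. A report that applied it as written could say that the 50% target had not been rejected at, say, 8 of 33, although the planned 95% interval would lie wholly below 50%.

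**Working it through.** **Inputs.** From section 5.1: n = 33, null rate 0.20, alternative rate 0.50, two-tailed exact binomial test, upper cut-off 12, lower cut-off 1, alpha 2.75%, power 95.99%. From section 5.1.3: two-sided 95% Clopper-Pearson interval. X is the number of responders among 33.

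**Step 1: reproduce the stated power and alpha.**

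- Power: P(X ≥ 12 | 0.5) = 0.9599, the stated 95.99%.
- Upper tail at 20%: P(X ≥ 12 | 0.2) = 0.02159.
- Lower tail at 20%: P(X ≤ 1 | 0.2) = 0.8^33 + 33 × 0.2 × 0.8^32 = 0.00063 + 0.00523 = 0.00586.
- Sum: 0.02159 + 0.00586 = 0.02745, the stated 2.75%.

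With the upper cut-off held at 12, no other treatment of the lower tail gives that alpha:

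| Lower rejection region | Total alpha at 20% |
|---|---|
| none | 2.16% |
| 0 | 2.22% |
| 1 or fewer | 2.75% |
| 2 or fewer | 4.84% |

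Also, P(X ≤ 2 | 0.2) = 2.68% exceeds 2.5%, so 1 is the lower 2.5% critical value for 20%.

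**Step 2: test the same count against 50%.** P(X ≤ 1 | 0.5) = (1 + 33) / 2^33 = 4.0 × 10^-9. The tail stays below 2.5% up to 10 successes: P(X ≤ 10 | 0.5) = 1.75% and P(X ≤ 11 | 0.5) = 4.01%. The lower boundary for 50% is therefore 10 at 2.5% per side, or 11 at a one-sided 5% level.

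**Step 3: compare with the planned interval.** For x of n, the lower limit is the 0.025 quantile of Beta(x, n − x + 1) and the upper limit is the 0.975 quantile of Beta(x + 1, n − x).

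| Successes of 33 | 95% Clopper-Pearson | Excludes 20%? | Excludes 50%? |
|---|---|---|---|
| 1 | 0.1% to 15.8% | yes, from below | yes |
| 2 | 0.7% to 20.2% | no | yes |
| 10 | 15.6% to 48.7% | no | yes |
| 11 | 18.0% to 51.8% | no | no |
| 12 | 20.4% to 54.9% | yes, from above | no |

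Both counts in section 5.1, 1 and 12, are boundaries for 20%. The boundary for 50% is 10. This is a restatement rather than independent evidence, because the interval inverts the same exact tail tests at 2.5% per side. It does show what the planned analysis would report.

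**Step 4: size of the zone from 2 to 10.** The upper limits there run from 20.2% to 48.7%, all below 50%. The chance of landing in the zone, for assumed true rates, is:

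- 20%: 1 − 0.0508 − 0.0059 = 94.3%, using P(X ≥ 11 | 0.2) = 0.0508
- 30%: 59.9%
- 50%: 1.75%

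**The case against.** The strongest reply has three parts.

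First, the sentence is literally true as a sufficient condition: 1 or fewer successes certainly rejects 50%, and nothing says that 2 to 10 would not. Section 5.1.3 plans an interval without comparing it with 50%. The clash therefore depends on reading the count as a boundary and the interval as a test of 50%. That dependence is real and should be acknowledged, but the sufficient-condition reading is strained, because the count is paired with 12, which is an exact critical value.

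Second, no decision hangs on the clause. It is introduced as an aside, and the protocol attaches no interim look or futility step to it. With 2 to 10 successes the null is not rejected on either reading. This stands and limits the weight of the point. The 94.3% and 59.9% are mostly the chance of an ordinary unsuccessful trial, not of a wrong conclusion on the primary endpoint.

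Third, relabelling the count as the lower critical value for 20% sits badly with a null written as 20% or less, since a low count cannot contradict that null. This also stands, and it favours deletion over relabelling.

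**Conclusion.** The concern holds. The 2.75% alpha can be obtained with the cut-off of 12 only if 1 or fewer is the lower rejection region for 20%, yet the text attaches that count to the 50% alternative. Every number in the section reproduces; the fault is that a threshold is assigned to the wrong hypothesis.

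The stated count is nine successes below the boundary implied by the planned interval (1 against 10 of 33). The effect is limited to the interpretation of results from 2 to 10 successes. The figure of 10 assumes 33 analysed subjects and the two-sided 95% level of section 5.1.3, because the protocol gives no level of its own for rejecting the alternative. The sample size of 33, the 42 recruited, the power, the alpha and the success cut-off of 12 are unaffected.

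**What to change.** Delete the clause on rejecting the alternative from section 5.1. This is the cleanest remedy given how the null is written. If the count is kept to explain the alpha, describe it as the lower critical value of the two-tailed test of 20% at n = 33.

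A rule for the 50% target is optional. If one is wanted, it could read: *The 50% target is excluded when the upper limit of the planned 95% Clopper-Pearson interval is below 50%.* That means 10 or fewer of 33, or 14 or fewer if all 42 are analysed (upper limit 49.5% at 14 and 52.0% at 15).

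The cost is one clause. No design figure, visit or procedure changes.
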